**Clinical effects analyses.** In order to estimate the possible effects of *Rose* on clinical outcomes, we will conduct two types of analyses. First, to estimate the immediate effects of the *Rose* sessions that target pain intensity, we will compute the ranges and average pre- to post-session changes in current pain intensity ratings for each participant individually (including participants in the Access condition who had access to 8 full weeks from baseline to the 8-week assessment point, and participants in the waitlist condition who had access for 4 weeks from the end of week 4 to the end of week 8 assessment point) and compute the median, minimum, and maximum of these values. Median statistics will be computed as the measure of central tendency given that the distributions of these changes were anticipated to be positively skewed (i.e., we anticipate that most participants would access *Rose* about four times during every 4-week period of access, but a fewer number might access *Rose* many times). Of interest is the general consistency of responses to the *Rose* sessions both within and between individuals. We will also conduct a linear mixed-effects model for the pre- to post-session change in pain intensity, including a random intercept for each participant to account for clustering (one for each study), to estimate the effect size and

significance levels of these changes. Given the possibility that participants who found *Rose* to be particularly effective may choose to listen to more sessions than those who found *Rose* to be less effective, as a sensitivity analysis, we will assess if there is evidence of informed cluster sizes by testing if the effectiveness of *Rose* is associated with the number of times sessions were listened to. This allows us to determine if the magnitude of the pre- to post-session improvements in pain intensity and mood are associated with frequency of listening (i.e., if those who reported more benefits tended to listen more often, which could bias the estimates of average benefit).

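### The ranges and extremes planned to describe consistency of session response also depend on how many sessions each participant rated

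*Combined protocol and SAP*

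**What the plan says.** The relevant text is the first part of Clinical effects analyses in the Statistical Analysis Plan. For pain ratings taken just before and just after a session, "we will compute the ranges and average pre- to post-session changes in current pain intensity ratings for each participant individually"; the next step is to "compute the median, minimum, and maximum of these values". Both arms contribute: Access participants "who had access to 8 full weeks from baseline to the 8-week assessment point" and Waitlist participants "who had access for 4 weeks from the end of week 4 to the end of week 8 assessment point". The purpose follows: "Of interest is the general consistency of responses to the *Rose* sessions both within and between individuals".

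Medians are chosen because the distributions of the changes are expected to be positively skewed. The explanation offered concerns how often people will listen, with heavy use by a minority: "we anticipate that most participants would access *Rose* about four times during every 4-week period of access, but a fewer number might access *Rose* many".

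Two further analyses follow. One is a linear mixed-effects model for the session change, with a random intercept per participant, fitted separately for each study to obtain an effect size and significance level. The other is a sensitivity analysis of whether the size of benefit is associated with the number of sessions. The Measures section adds that ratings are collected only around sessions containing suggestions for comfort, so the number of rated sessions may be smaller than the number listened to.

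**The concern.** The range is the only within-person measure of spread that the plan names, and a range is tied to the number of observations behind it. Adding a session can leave it unchanged or widen it, but never narrow it. With one rated session it is 0 whatever the person's true variability. The plan sets no minimum number of sessions and makes no adjustment for session count, although it expects counts to differ widely between people and the access windows are 8 and 4 weeks.

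The between-person summary has a related weakness. An average over one or two sessions is noisy, so the minimum and maximum of the participant averages tend to come from people who used Rose least.

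The reason for the median does not fit either. It describes skew in how often people listen, whereas the quantities being summarised are pain changes. One does not imply the other.

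At stake is a descriptive result meant to inform a full trial. A regular user and an occasional user with the same true variability would tend to show different ranges, and the spread between people would look larger than it is.

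**Working it through.** The documents give no figure for this point, so there is none to reproduce.

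**Inputs from the plan.** About 4 sessions per 4-week period of access, hence about 4 over 4 weeks and 8 over 8 weeks, with some heavy users. Ratings are whole numbers from 0 to 10.

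**Assumptions (not in the documents).** Within-person SD of the session change 1.0, 1.5 or 2.0 points; true between-person SD of the mean change 0.7; others as stated below.

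**Step 1: expected range at fixed variability.** For n independent normal changes with common SD σ, E[range] = σ × ∫{1 − Φ(x)ⁿ − (1 − Φ(x))ⁿ}dx. The integral is 0, 1.128, 2.059, 2.847 and 4.586 for n = 1, 2, 4, 8 and 56, where 56 is daily use for 8 weeks.

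- 8 against 4 sessions: 2.847/2.059 = 1.38, whatever the value of σ.
- 56 against 4 sessions: 4.586/2.059 = 2.23.

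| σ | n = 4 | n = 8 |
|---|---|---|
| 1.0 | 2.06 | 2.85 |
| 1.5 | 3.09 | 4.27 |
| 2.0 | 4.12 | 5.69 |

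**Step 2: whole-number ratings bounded at 0 and 10.** With an assumed pre-session mean of 5.5 (SD 1.5) and a mean change of −1.5, simulated mean ranges at n = 4 and n = 8 are 2.04 and 2.82 (σ = 1.0), 3.02 and 4.17 (1.5), and 3.93 and 5.39 (2.0). The bounds dampen the growth only slightly.

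**Step 3: skewed session counts.** With negative binomial counts (mean 4 or 8, dispersion 1 or 2), σ = 1.5 and identical true variability for everyone, range and session count correlate at 0.64 to 0.69. Between 7% and 20% of users have one session and so a range of 0.

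**Step 4: averages between people.** SD of a participant's average = √(0.7² + σ²/n).

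- σ = 1.0: √(0.49 + 1.00) = 1.22 at n = 1; √(0.49 + 0.125) = 0.78 at n = 8.
- σ = 1.5: √(0.49 + 2.25) = 1.66; √(0.49 + 0.281) = 0.88.
- σ = 2.0: √(0.49 + 4.00) = 2.12; √(0.49 + 0.50) = 0.99.

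The true between-person SD is 0.7 throughout. In a simulated study of 50 with log-normal weekly use (mean 1 per week, log SD 0.8; 25 people with 8 weeks of access and 25 with 4) and σ = 1.5, people with one or two sessions were 27% of users but supplied 64% of the minimum and maximum averages. The gap between those extremes averaged 5.3 points, against 3.1 for the true person means. For σ = 1.0 and 2.0 the share was 52% and 70%, and the gap 4.2 and 6.6.

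**Step 5: an alternative.** In the simulation of Step 2 with σ = 1.5, the pooled within-person SD (root of the mean within-person variance) stayed at 1.49 to 1.50 from n = 2 to n = 56, while the mean range rose from 1.66 to 6.62. The mean of individual SDs is low at small n: 1.17 at n = 2, 1.38 at n = 4, 1.44 at n = 8.

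**The case against.** The plan does not say that consistency is judged by the range. It lists descriptive statistics and then calls consistency of interest, with no index, threshold or test. Ranges may simply mean each person's lowest and highest change, which is a legitimate display and shows, for example, whether any session was followed by worse pain. This stands. The link between range and consistency is an inference, drawn because no other within-person measure of spread is named.

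A reader might infer that the Access arm will look less consistent than Waitlist. The documents do not support that as a consequence of the plan. This passage describes the arms together and plans no comparison of consistency by arm; the stratified tables described later concern means and SDs at the assessment points. An arm difference would appear only if ranges were read by arm and Access users rated more sessions.

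A reader might also infer that the range measures only how much Rose was used. That goes too far. When true within-person SD was allowed to vary (assumed log SD 0.3 to 0.5), the range correlated about 0.4 to 0.6 with true SD and about 0.4 to 0.6 with session count. It is confounded by use but still informative. Nor does it widen with every session; only its expectation rises.

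Finally, the planned mixed model yields variance components as standard output. True, but the plan states another purpose for that model and does not commit to reporting them. The sensitivity analysis relates size of benefit, not spread, to session count, so it does not deal with the problem.

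**Conclusion.** The point holds as a minor one. For a question the plan itself poses, the named summaries mix consistency with number of rated sessions. Under independent normal changes with equal variability, the expected range is 38% wider at 8 sessions than at 4, and this ratio does not depend on the SD. The differences in points do: about 0.8 to 1.6 across assumed SDs of 1.0 to 2.0 (2.85 − 2.06 = 0.79; 5.69 − 4.12 = 1.57). The inflation of the extreme averages rests further on the assumed between-person SD and pattern of use. The mismatch between the reason given for the median and the quantity summarised is visible in the text and needs no assumption.

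No feasibility criterion uses these summaries, and neither the mean-change estimates nor the between-group effect sizes change.

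**What to change.** In Clinical effects analyses:

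1. State that consistency will be assessed from the planned random-intercept model, with the session change score as the outcome. Report for each study the residual SD (within-person), the random-intercept SD (between-person) and the ICC, each with a 95% CI.
2. Keep each participant's lowest, highest and average change as description if wanted, shown beside the number of rated sessions. Do not interpret a range for anyone with one rated session.
3. Replace the reason for the median with one about the distribution of the pain changes, or drop it.

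The residual SD is a single pooled figure that assumes similar variability across people, which is why the individual display in item 2 is worth keeping.

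The cost is a change of wording. The model is already planned and the application already records the sessions and ratings.

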## **Study Protocol and Statistical Analysis Plan**

**Title: Digital Clinical Hypnosis for Chronic Pain Management**

**NCT number: NCT06050083**

**Document date: 08/21/2025**

## Study Protocol

### Overview of Study 1 and Study 2

This protocol describes two studies that are a part of this project. They use the same experimental design to evaluate the feasibility of the digital program. The primary difference is that first study (Study 1) recruits individuals with chronic low back pain and the second (Study 2) recruits individuals with general chronic pain (which includes individuals with chronic low back pain as well as individuals with chronic pain as a secondary condition to another health problem, such as spinal cord injury). Both studies aim to enroll 50 participants, which, given an estimated 20% dropout rate, would allow for complete data from at least 40 participants in each study.

Both studies use a 2-arm prospective randomized controlled trial design to evaluate the feasibility of the program (called *Rose*) over an 8-week period. Participants are randomly assigned to one of two groups: *Rose* access for a full 8 weeks (Access group) or *Rose* access for 4 weeks (Waitlist control group). The Waitlist group will not have access to *Rose* for the first 4 weeks of the study and then have access to *Rose* for the final 4 weeks. The 4-week assessment point is the primary study endpoint. Primary (feasibility) and secondary (clinical) outcomes using the *Rose* program and self-report measures using the Research Electronic Data Capture (REDCap) program, hosted by the University of Washington Institute of Translational Health Sciences (ITHS). Participants complete the self-report measures at three timepoints: baseline (before randomization), 4 weeks after randomization (primary endpoint), and 8 weeks after randomization.

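### A single association test in about 40 people per study cannot show that the mixed-model estimate of immediate pain relief is free of bias from heavier listeners; a participant-weighted mean with a 95% CI should stand beside it

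*Combined protocol and SAP*

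**What the plan says.** The immediate effect of a session is handled in the Statistical Analysis Plan under Clinical effects analyses, in three steps.

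1. The plan computes the "average pre- to post-session changes in current pain intensity ratings for each participant individually", and summarises those values by their median, minimum and maximum.
2. It also fits a linear mixed model to the session changes, "including a random intercept for each participant to account for clustering (one for each study"). This is the analysis that supplies an effect size and a significance level.
3. Because satisfied users may choose to listen more, a sensitivity analysis is added: "we will assess if there is evidence of informed cluster sizes by testing if the effectiveness of" Rose goes with the number of sessions heard. The plan then explains its purpose: "This allows us to determine if the magnitude of the pre- to post-session improvements in pain intensity" (it adds mood) go with listening frequency, and it notes that such a link could bias the average.

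The plan gives no form of test, alpha, detectable association or interval for the association, and no action after either result.

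On size, the Overview sets an enrolment target of 50 per study. With dropout put at 20%, it reckons that this target "would allow for complete data from at least 40 participants in each study". The Measures section adds that the studies are not powered for clinical outcomes, and that pain is rated before and after only those sessions that contain suggestions for comfort.

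**The concern.** The plan identifies a real bias and then relies on a significance test to look for it. A random-intercept model gives more weight to participants with more sessions. If those participants also benefit more, the model mean lies above the average listener's benefit. A test in about 40 people, fewer if some never listen, has limited power against such a link, and non-significance is weak evidence that the link is absent. The plan describes the test as letting the investigators determine the matter, which invites more confidence than the test can supply.

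At stake is how far the immediate-effect estimate, one of the results meant to inform a full trial, can be trusted as the benefit to a typical listener. The plan has no second estimate of the mean, with an interval, that is protected against this bias.

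**Working it through.** **1. Sample size (from the documents).** 50 × (1 − 0.20) = 40 complete per study, which matches the Overview. The model is fitted separately in each study, so 40 is the relevant number, with a maximum of 50.

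**2. How much extra weight heavy listeners get.** In a random-intercept model, participant i with n_i sessions has weight proportional to 1/(σ_b² + σ_w²/n_i). The documents give neither SD. Assume a between-person SD σ_b = 1.0 and a within-person SD σ_w = 1.5 NRS points:
- 4 sessions: 1/(1 + 2.25/4) = 0.640
- 25 sessions: 1/(1 + 2.25/25) = 0.917

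The ratio is 0.917/0.640 = 1.43. Pooling all sessions would give 25/4 = 6.25. The model therefore leans towards heavy listeners, but far less than raw pooling. With σ_b = 0.5 and σ_w = 2 the ratio is (1/0.41)/(1/1.25) = 3.05, so the problem grows when people differ little and sessions are noisy.

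**3. Power for an observed correlation r.** By Fisher's z, with two-sided alpha 0.05 assumed, power ≈ Φ(atanh(r)·√(n − 3) − 1.96). For n = 40 and r = 0.3: Φ(0.3095 × 6.083 − 1.96) = Φ(−0.077) = 47%.

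| n | r = 0.3 | r needed for 80% power |
|---|---|---|
| 30 | 36% | 0.49 |
| 40 | 47% | 0.43 |
| 50 | 56% | 0.39 |

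At n = 40 the power is 23% for r = 0.2, 73% for r = 0.4 and 92% for r = 0.5.

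**4. Observed against latent correlation.** The bias comes from the link with true benefit, and the test sees noisy averages. With 4 sessions and SDs of 1.0 and 1.5, the reliability of an average is 1/(1 + 2.25/4) = 0.64. A latent 0.5 is then seen as at most 0.5 × √0.64 = 0.40, before any noise in the counts. In simulation at these SDs the observed value was 0.26–0.28.

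**5. Simulation, 40 participants, 1,500 studies per scenario.** All variance inputs are assumptions.
- *Set-up A*: SDs 1.0 and 1.5; skewed counts with median about 4, mean about 6 and maximum about 25; true average benefit 0; log count tested as a covariate in the model.
- *Set-up B*: between-person SD 0.5–1.5; within-person SD 1–2; mean sessions 8 (Access) and 4 (Waitlist); coefficient of variation of counts 0.8–2.5; mean change 1.5; people with no sessions dropped (about 34–38 of 40 listen at CV 0.8–1.5). Bias is measured against the equal-weight mean of listeners' true effects.

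| Latent correlation | Power, A | Power, B | Model bias, A | Model bias, B |
|---|---|---|---|---|
| 0.3 | 24% | 10–22% | 0.08 | 0.02–0.08 |
| 0.5 | 57% | 18–55% | 0.14 | 0.05–0.13 |
| 0.7 | not run | 27–87% | not run | 0.06–0.19 |

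Bias is in NRS points. The model SE was 0.20–0.21 in A and 0.13–0.27 in B. With 50 participants, power in A rises to 27% and 67%. The largest bias in B, 0.19, is 0.19/1.5 = 13% of the assumed change.

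**6. What a null result tells you.** In B the bias against the truth hardly changes when only non-significant tests are kept. With SDs 1.0 and 1.5, count CV 1.5 and correlation 0.5, it is 0.113 after a null and 0.108 overall.

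**7. The participant-weighted mean.** Its bias was −0.01 to +0.01 in B and −0.004 and 0.002 in A. Its SE relative to the model's:
- A: 0.214/0.200 = 1.07 and 0.223/0.206 = 1.08
- B, both SDs 1 and CV 1.5: 0.198/0.193 = 1.03
- B, SDs 0.5 and 2, CV 2.5, correlation 0.3: 0.252/0.185 = 1.36

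The planned median of participant averages was off by up to about 0.09 in B as an estimate of the mean.

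**The case against.** The strongest reply is that the plan claims little. Immediate pain change is one of six secondary clinical domains in feasibility studies that are declared not to be powered for clinical outcomes, and no feasibility criterion uses this model. The plan openly warns of the bias, and its participant-level median is already unweighted by session count. All of that stands, and it sets the priority.

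Three stronger readings are tempting, and the documents do not support them.

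- *A null test would be taken to validate a headline estimate.* The plan names no headline estimate. The participant summary comes first and the model is introduced as an addition. Nowhere does the plan say that a null clears the model. Giving the model precedence is an inference from its carrying the effect size and significance level.
- *The test usually misses the problem.* That holds for weak links. At a latent 0.5 the result depends on the assumptions (57% detected in A, 18–55% in B), and a strong link is often found unless within-person noise dominates.
- *The plan risks declaring an effect that does not exist.* In A at correlation 0.5, the model declared an effect in 13% of studies and its 95% CI covered 87%. That requires a true average benefit of exactly zero. With an assumed 1.5-point change, SDs of 1.0 and 1.5 and mean counts of 8 and 4, the effect was significant in essentially every run, so no conclusion changed.

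The remedy has limits too. People who never listen have no change score. In those same runs with a 1.5-point change, at correlation 0.5, listeners' true mean already exceeded that of all participants by 0.10 points, and no weighting of listeners corrects that. The gap between the two estimates is also imprecise. In A it averaged 0.06–0.08 among null tests, against 0.081 + 0.004 = 0.085 and 0.144 − 0.002 = 0.142 overall, so a small gap is not proof of no bias either.

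**Conclusion.** The point holds in a limited form. The association test cannot establish that the mixed-model estimate is free of bias from informative cluster size: it often misses weak to moderate links, and the bias that remains after a null is essentially undiminished. The bias itself is modest, under 0.2 NRS points in every scenario examined and mostly below one standard error; the exceptions were at a latent correlation of 0.7 with small between-person variance. The planned median offers partial protection, with about half the model's bias, but it comes without an interval or a stated comparison.

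These sizes rest on assumed SDs, session counts, correlations and alpha, none of which the documents give. That a null result is weak evidence of absence at this sample size does not depend on the particular values. This is an inexpensive improvement of minor priority.

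**What to change.** In the Statistical Analysis Plan, Clinical effects analyses:

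1. Whatever the test shows, report beside the mixed-model estimate the mean of the participants' own average changes, one vote per participant, with its 95% CI. Treat the gap between the two as the sensitivity result, without making it a pass/fail rule.
2. Report the benefit–listening association as a slope with a 95% CI, and call the test exploratory.
3. State that a non-significant result does not show absence of informative cluster size.
4. State that both estimates apply only to people who listened to at least one rated session.

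Nothing planned is removed. The participant averages are already computed, so the cost is a few sentences and one or two lines of output. The downside is a somewhat wider interval: typically about 2–8% under these assumptions, and up to about 36% with very skewed counts and small between-person variance.

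### The plan tests whether session benefit is linked to session count but gives no estimate that allows for such a link, and a null test result would not show that the mixed model is safe

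*Combined protocol and SAP*

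**What the plan says.** In the SAP under Clinical effects analyses, the inferential estimate of immediate benefit is described as follows: "We will also conduct a linear mixed-effects model for the pre- to post-session change in pain intensity, including a random intercept for each participant". One model is fitted per study, to give an effect size and significance levels.

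The same paragraph recognises that those who find the program more effective may choose to listen more. As a sensitivity analysis it will test whether effectiveness "is associated with the number of times sessions were listened to". The stated purpose is to learn whether "improvements in pain intensity and mood are associated with frequency of listening", because a link of that kind is something "which could bias the estimates of average benefit".

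The paragraph gives no weighted or otherwise corrected estimate, and no rule for what follows a positive or a negative test. It does plan a descriptive summary in which each participant's average change is computed and the median and extremes across participants are shown. That summary has no interval. The section plans confidence intervals only for the between-group effect sizes, and says that no rigorous significance testing will be done there.

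**The concern.** A sensitivity analysis should show how far the answer moves when an assumption fails. This one only asks whether there may be a problem. If the test is positive, the reader knows the model's average is suspect but has no better estimate. If it is negative, the model will probably be taken as sound, although a study of this size could easily miss a moderate link.

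The predictor adds a difficulty. Session counts accumulate over 8 weeks in Access and 4 weeks in Waitlist, so at the same weekly use the count differs twofold by arm. The plan nevertheless reads the result as being about frequency.

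At stake is the size of the average session benefit. It is a secondary result, but the Measures section says the clinical estimates are meant to inform a full trial.

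**Working it through.** **Sample size.** The Overview of Study 1 and Study 2 states: "Both studies aim to enroll 50 participants", with "given an estimated 20% dropout rate". Then 50 × (1 − 0.20) = 40, which reproduces the plan's own figure. I take 40 as the number of listeners per study. This is an assumption, because the figure refers to complete data and not to listening; 32 and 50 are shown as a range.

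**Power of the association test.** No power and no alpha are stated for it; I assume two-sided 0.05. By the Fisher z approximation, power ≈ Φ(atanh(r) × √(N − 3) − 1.96). For N = 40 and r = 0.3: 0.3095 × 6.083 − 1.96 = −0.077, so power is 47%.

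| Listeners | r = 0.2 | r = 0.3 | r = 0.4 | r = 0.5 | r for 80% power |
|---|---|---|---|---|---|
| 32 | 19% | 39% | 63% | 84% | 0.48 |
| 40 | 23% | 47% | 73% | 92% | 0.43 |
| 50 | 28% | 56% | 83% | 97% | 0.39 |

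Here r is the correlation with observed mean change. Session noise makes it weaker than the correlation with true benefit.

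**Weighting.** In a random-intercept model of change scores, a participant with n sessions has weight 1/(τ² + σ²/n), where τ is the between-person SD and σ the within-person SD. With assumed τ = 1.0 and σ = 1.5:
- 40 sessions: 1/(1 + 2.25/40) = 0.947
- 4 sessions: 1/(1 + 2.25/4) = 0.640
- ratio: about 1.5, not 10

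Heavier listeners count for more than in a per-person average, but far less than in proportion to their sessions.

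**Size of the bias, by correlation.** Simulation with REML, 1000 runs per setting. Assumed: 40 or 50 listeners, typical use of 8 sessions (Access) or 4 (Waitlist) with log-normal spread of SD 0.9, mean benefit 1.5 NRS, τ 0.5 to 1.5, σ 1.0 to 1.5, and correlation ρ between true benefit and log use.

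| ρ | Model bias (NRS) | Coverage of a nominal 95% interval | Power, raw-count test |
|---|---|---|---|
| 0.2 | 0.02–0.06 | 92–95% | 9–18% |
| 0.3 | 0.04–0.08 | 90–94% | 12–32% |
| 0.5 | 0.07–0.12 | 83–93% | 24–70% |

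The equally weighted mean of participant means had bias of at most about 0.01 and coverage of 93–96% throughout.

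**Size of the bias, by listening multiplier.** Simulations with 40 listeners, about one session per week, mean change 1.0 NRS and several assumed spreads of use:
- 1 SD more benefit multiplies listening by 1.35: model bias 0.07–0.15, coverage 85–91%, raw-count power 17–41%.
- Multiplier 1.8: bias 0.14–0.24, coverage 71–82%, power 40–85%.
- Equally weighted mean: bias at most 0.05, coverage 93–96%.
- Sessions per week of access instead of the raw count: about 3 to 12 points more power.

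**Shift or narrow interval?** At the 1.35 multiplier, one set of runs gave a mean model SE of 0.145–0.218 against an empirical SD of 0.154–0.229, so the SE is only about 3–6% low. In one correlation setting (40 listeners, τ 1.0, σ 1.5, ρ 0.5) the bias was 0.117 and the SE 0.189, a ratio of 0.62. The shift alone then gives coverage of Φ(1.96 − 0.62) − Φ(−1.96 − 0.62) = 0.910 − 0.005 = 0.905; the simulated value was 0.894. Nearly all of the loss comes from the shifted centre.

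**Rejection of zero.** At a mean change of 1.0 and the largest SE above, 1.0/0.218 = 4.6 standard errors. Both estimators rejected zero in at least 94% of runs in every setting.

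**The case against.** The strongest reply has four parts.

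- The random intercept already limits the pull of heavy listeners, as the ratio of 1.5 shows. This stands, and it is why the bias is small to modest.
- Power is good where bias matters most: 92% at an observed correlation of 0.5 with 40 listeners. This stands for strong links. It does not help with moderate ones, and a positive test still leads to no corrected estimate.
- The participant-level median summary counts each listener once, so a gap from the model mean could be noticed. It is a real but partial safeguard, without an interval.
- A per-session average is a legitimate target, and the plan does not say which average it wants. True, but the plan's worry about bias makes sense only for a per-person average, and the mixed model weights lie between the two.

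A reader might also infer more than the documents support:

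- That the model's 95% CI is wrong or too narrow. The plan promises no CI for this model, and the SE is close to right. The coverage figures above only describe what a nominal interval would do.
- That the significance of the session effect is in doubt. At the assumed mean changes it is not.
- That each session counts equally, with far larger bias. That would need a model of the raw pre and post ratings with only a random intercept. The plan describes a model for the change, so this is not the natural reading.
- That the feasibility conclusions are affected. None of the five feasibility criteria uses this estimate.

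**Conclusion.** The point holds as a modest gap in a secondary analysis. The plan names a bias, only tests for it, and keeps one inferential session-level estimate whichever way the test falls. With about 40 listeners per study, a non-significant test does not clear the model. Under assumed moderate associations the average benefit is overstated by roughly 0.05 to 0.15 NRS points; larger values, up to 0.24 in the settings tried, need strong associations that no document supports.

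The direction follows from the weighting and from the mechanism the plan itself describes. The size rests on assumed benefit, variances, use and association. The conclusion that rejection of zero is unaffected rests on an assumed mean change of 1.0 NRS or more.

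**What to change.** Add one or two sentences to Clinical effects analyses:

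- Whatever the association test shows, report for each study, beside the mixed model, the mean pre- to post-session change that weights each listener equally, with a 95% CI. Either the mean of participant means with a t interval, or GEE weighted by 1/number of sessions with robust SE, would do.
- Base any statement about average benefit per listener on that estimate.
- In the association test, use sessions per week of access, or adjust for arm.

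No new data are needed, only a few lines of code. The price is an SE about 5% to 25% larger, depending on the spread of use and on session noise. The estimate still describes only people who listened at least once, and the report should say so.
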